**Table LLCF.SAP.1. Analysis Populations for Study I7X-MC-LLCF**

Population Name	Description of Population
Enrolled	All participants who have been assigned to treatment (randomized).
Efficacy	All randomized participants who take at least 1 dose of double-blind study treatment and have at least 1 postdose efficacy measurement.
Safety	All randomized participants who take at least 1 dose of double-blind study treatment.
Per-Protocol	All subjects in the Full Efficacy population who also: 
 
• had an assessment of the primary endpoint at each scheduled visit completed
 
• had no violations of inclusion/exclusion criteria
 
• had no study dosing algorithm violation (such as if subjects randomized to treatment A were given treatment B or subjects randomized to treatment A never received the assigned study drug)
 
• had no unqualified raters and no raters with substantial scoring errors for the primary measure
 
• was not considered non-compliant with regard to study drug
 

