Abbreviations: Aβ = amyloid beta peptide; ADAS-Cog₁₃ = 13-item Alzheimer's Disease Assessment Scale – Cognitive subscale; ADCS-ADL = Alzheimer's Disease Cooperative Study-Activities of Daily Living inventory; APOE = apolipoprotein E; BASQID = Bath Assessment of Subjective Quality of Life in Dementia; C-SSRS = Columbia-Suicide Severity Rating Scale; ECG = electrocardiogram; ECog = Everyday Cognition; ED = early discontinuation; EDTA = ethylenediaminetetraacetic acid; FAQ = Functional Activities Questionnaire; MMSE = Mini-Mental Status Examination; MoCA = Montreal Cognitive Assessment; MRI = magnetic resonance imaging; NIA-AA = National Institute on Aging-Alzheimer's Association; NPI = Neuropsychiatric Inventory; PD = pharmacodynamics; PET = positron emission tomography; PK = pharmacokinetics; R&D = research and development; RNA = ribonucleic acid; V = visit.

^a Every effort should be made for visits to occur on the designated study days. The overall treatment period in the protocol should be maintained (that is, visits should be scheduled based on the baseline visit rather than the previous visit). Study procedures designated for a specific visit should be performed within 1 day whenever possible. If the time spent at the site needs to be minimized, the assessments can be completed over a longer period.

- b Visit 1 takes place over more than 1 day. Clinical scales should be administered before imaging procedures are conducted.
- Only capture imaging measures (MRI, florbetapir F 18 PET, and ¹⁸F-AV-1451 PET) at the ED visit if at least 24 weeks have passed since the baseline measurement was obtained. Note: Patients should be encouraged to remain in the study after their ED Visit until Week 52 (Visit 18), even if study treatment has been discontinued. Patients who discontinue treatment, but remain in the study should continue to participate in all scheduled visits and assessments, as appropriate, with the exception of PK measurements and PET scans. The follow-up visit (Week 56) is not required for patients who discontinue study treatment early and continue in the study, unless the study drug was discontinued within that last 4 weeks of the study.
- d Screening period exceeding 60 days will not be considered a protocol deviation. If the screening period exceeds 120 days, sites should contact the Lilly-designated medical monitor for guidance.

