7.1.1. Packaging and Labelling

Study drug will be supplied as 3-mg and 12-mg capsules. The study drug and placebo will be identical in appearance and will be packaged in bottles. Clinical trial materials will be labeled according to the country's regulatory requirements.

7.1.2. ¹⁸F-AV-1451 Dosage and Administration

A total of 2 ¹⁸F-AV-1451 PET scans will be performed, approximately 52 weeks apart. The baseline ¹⁸F-AV-1451 scan should not be performed until a positive florbetapir F 18 PET result has been confirmed by central read and all other screening criteria have been confirmed. The Visit 18 or early discontinuation florbetapir F 18 and ¹⁸F-AV-1451 scans must be at least 16 hours apart. At each ¹⁸F-AV-1451 PET scanning visit, patients will receive a single intravenous (IV) administration of approximately 370 MBq (10 mCi) of ¹⁸F-AV-1451. A 30-minute scan, starting approximately 75 minutes following injection, will be acquired according to the procedure described in the technical operations manual provided by the designated imaging core laboratory.

Patients with a history of risk factors for Torsades de Pointes or taking prohibited medications known to prolong the QT interval should not have a ¹⁸F-AV-1451 scan. Patients permanently discontinued from study treatment due to initiation of a prohibited medication known to prolong the QT-interval should not have an early discontinuation (ED) ¹⁸F-AV-1451 scan unless the scan can be performed prior to initiation of the prohibited medication.

The following assessments will be performed for ¹⁸F-AV-1451 imaging sessions:

- A physician or a licensed/credentialed medical professional (for example, a PET Technologist or an imaging center nurse) designated by the site Principal Investigator (PI), must assess or evaluate the patient to determine if the patient can safely undergo a ¹⁸F-AV-1451 injection. If a designee performs this activity, a physician must be available to provide medical consultation or supervision.
- The patient will be requested to void after completion of the PET scan.
- A physician or a licensed/credentialed medical professional designated by the site PI must assess or evaluate the patient prior to discharge from the imaging center to evaluate the patient's readiness for discharge. If a designee performs the discharge evaluation, a physician must be available to provide medical consultation.

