### 3. Revision History

Statistical Analysis Plan (SAP) Version 1 was approved prior to unblinding.

Statistical Analysis Plan (SAP) Version 2 was approved prior to final database lock. Due to early termination of the study, certain analyses were removed or simplified, while others were clarified. The changes in SAP version 2 are summarized below:

- Clarified that change from baseline to last observation is to be used in ANCOVA analysis if Week 52 observation is not available (Section [5.1](#))
- Removed the exploratory analysis on subjects with study partner change during the study (previously Section 5.11 in Version 1)
- Clarified the analysis for changes from baseline in NPI total score and BASQID total score will be ANCOVA instead of MMRM because they were collected only once during post-baseline visits (Section [5.11.2](#))
- Specified the cut-off for defining Tau subgroups and removed the subgroup analysis regarding race and country (Section [5.11.3](#))
- Removed sensitivity analysis on Tau PET using percentage changes from baseline (previously Section 5.12.4 in Version 1)
- Simplified analysis of CSF biomarkers to listing of values by visit by treatment due to very limited number of subjects participated in the CSF addendum (Section [5.12.2](#))
- Added analysis on annualized change in imaging biomarkers (vMRI, AV-45 PET, AV-1451 PET) because majority of the subjects would not have Week 52 observation due to early termination of the study (Section [5.12.5](#))
- Added an incidence summary for treatment-emergent CSSRS findings (Section [5.13.8.1](#))
- Simplified and clarified the analysis for categorical eye exam and eye imaging data (Section [5.13.8.3](#))

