## 5. A Priori Statistical Methods

### 5.1. General Considerations

All tests of treatment effects of biological efficacy or clinical efficacy will be conducted at a 1-sided  $\alpha=.10$ , unless otherwise stated. Safety assessments will be conducted at a 2-sided  $\alpha=.05$ .

A repeated measures analysis refers to a restricted maximum likelihood (REML)-based, mixed effects repeated measures analysis using all the longitudinal observations at each post-baseline visit.

All analyses will follow the intent-to-treat (ITT) principle unless otherwise specified. An ITT analysis is an analysis of data by the groups to which subjects are assigned by random allocation, even if the subject does not take the assigned treatment, does not receive the correct treatment, or otherwise does not follow the protocol.

When change from baseline is assessed, subjects will be included in the analysis only if both a baseline and a postbaseline measure are available. Unless otherwise defined, Visit 3 is the baseline visit, and baseline value is defined as last value available before or at Visit 3.

All total and subscale scores will be derived from individual items. If any individual item is missing, the corresponding total and subscale scores will be considered missing, except for the ADAS-Cog13 and ADCS-iADL, which will be imputed.

A repeated measures analysis model will include the fixed, categorical effects of treatment, visit, and treatment-by-visit interaction, as well as the continuous, fixed covariates of baseline, baseline-by-visit interaction, and age at baseline.

When an analysis of covariance (ANCOVA) model is used to analyze a continuous efficacy variable, the model will contain the main effects of treatment with baseline value and age at baseline added as covariates. For ANCOVA analysis on change from baseline to Week 52 endpoint, change from baseline to last observation during treatment period will be used if patients do not have Week 52 observation available.

Categorical comparisons between treatment groups will be performed using Fisher's exact tests or logistic regression where appropriate.

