### **5.6. Population for Analysis**

The Efficacy population is defined as all randomized participants who take at least 1 dose of double-blind study treatment and have at least 1 postdose efficacy measurement, which is used to assess the effectiveness of the study drug regimen; all observed data will be included (including data gathered after a subject discontinues study drug).

In order to assess the study drug treatment effect, data gathered after a subject discontinues study drug will not be included in the analysis of per protocol population.

Additionally, when change from baseline is assessed, subjects will be included in the analysis only if both a baseline and at least 1 valid post-baseline measure are available.

All subjects who received at least 1 dose of randomized study treatment (LY3202626 or placebo) will be included in the safety analysis set. If an LY3202626 dose group is dropped following an interim analysis, subjects switched to the remaining LY3202626 dose and remaining on treatment will be accounted for as a separate group.

For the Lumbar Puncture addendum, the analysis sets will include all those subjects whose eligibility was determined by the respective biomarker, who signed consent for addendum, and who have a baseline and at least 1 valid post-baseline cerebrospinal fluid (CSF) assessment.

The PK analysis set is defined as all subjects in the safety population who have at least 1 post-dose PK assessment. The population PK analyses will be performed using this analysis set.

The primary and secondary efficacy measures will be analyzed using the efficacy population unless otherwise specified. In addition, the primary measure will be analyzed using per-protocol populations to verify the robustness of the results. Summaries and analyses for safety measures will be based on the safety population.

[Table LLCF.SAP.1](#) below defines each of the analysis populations used in this study.

[Table LLCF.SAP.2](#) lists the study measures that will be summarized and/or analyzed for each population.

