#### **5.15. Protocol Violations**

Listings of subjects with significant protocol violations will be provided for the Full Efficacy population. The following list of significant protocol violations will be determined from the clinical database and from the clinical/medical group:

- Did not have an assessment of either the primary endpoint at any of the visits at which the scales were scheduled to be assessed.
- Protocol violations of inclusion/exclusion criteria.
- Had a study dosing algorithm violation (such as if subjects randomized to treatment A were given treatment B or subjects randomized to treatment A never received the assigned study drug.)
- Had unqualified raters or raters with substantial scoring errors for the co-primary measures.
- Was not compliant with regard to study drug.

The analyses for the primary objective will be repeated for the per protocol subject population.

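### SAP version 2 adapted the primary tau PET analysis to early termination but left the per-protocol and violation criteria tied to the Week 52 scan

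*SAP*

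**What the plan says.** The first per-protocol condition in Table LLCF.SAP.1 is that the patient "had an assessment of the primary endpoint at each scheduled visit completed". SAP 5.6 gives the purpose of the set: "the primary measure will be analyzed using per-protocol populations to verify the robustness of the results". SAP 5.15 repeats the primary analysis in this population. It also opens its list of significant violations with patients who "Did not have an assessment of either the primary endpoint at any of the visits at which the scales were scheduled to be assessed".

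The primary endpoint is change in tau PET SUVr. Protocol 7.1.2 says that two such "PET scans will be performed, approximately 52 weeks apart". The Schedule of Activities (Protocol Section 2) marks them at Visit 2 and Visit 18 (Week 52). It also marks the early discontinuation (ED) visit, where imaging is captured only "at the ED visit if at least 24 weeks have passed since the baseline measurement was obtained". Patients who stop treatment and stay in the study have no further PET.

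The revision history (SAP Section 3) records that the "majority of the subjects would not have Week 52 observation due to early termination of the study", and adds annualized change in the imaging biomarkers for that reason. SAP 5.1 sets the rule for the ANCOVA: "change from baseline to last observation during treatment period will be used if patients do not have Week 52 observation available". The revision history lists no change to the per-protocol definition or to 5.15.

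**The concern.** Version 2 moved the primary analysis to whatever on-treatment scan is available, but its robustness check still asks for the scan that the same document says most patients lack. On the plain reading, patients leave the per-protocol set because the study was stopped and not because they departed from the protocol. A per-protocol analysis is meant to show whether the result survives removal of patients who did not follow the plan. Here the main filter would be whether the patient had reached Week 52 when the study ended. A difference between the two analyses could then reflect shorter follow-up, smaller numbers or non-adherence, and could not be attributed to any one of them. The violation listing raises a related question, because its first item is worded differently and can be read in two ways.

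**Working it through.** **1. Who enters which analysis.** This takes the plain reading of the first per-protocol condition (scans at Visit 2 and Visit 18) and assumes that an ED scan falls within the treatment period.

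| Patient has baseline scan and | Primary ANCOVA (SAP 5.1) | Per-protocol |
|---|---|---|
| Week 52 scan | in | in, if the other conditions are met |
| ED scan at 24 weeks or later, no Week 52 scan | in, by last observation | out |
| no post-baseline scan | out | out |

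The middle row is the mismatch.

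**2. Overall size.** The plan's own figures reproduce: 380 × (1 − 0.15) = 323 against about 320 completers; 320 / 0.85 = 376.5, so 377, against 380; and 167 + 167 + 45 = 379. If a majority lack Week 52, fewer than half can qualify. At the planned 380 that is fewer than 190 patients, against about 320 planned completers. The number randomized when the study stopped is not given.

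**3. By arm.** The text fixes no split. Two calculations at 380 randomized, with half (190) lacking Week 52:

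- Lowest share for 12 mg and placebo together, if all 45 patients on 3 mg are among those lacking it: (190 − 45) / (380 − 45) = 145/335 = 43%.
- If patients reach Week 52 strictly in order of enrolment, with 1:1:1 allocation until 3 × 45 = 135 are in: the first 190 comprise 45 on 3 mg and 145 on the other arms, so 1 − 145/335 = 57% of 12 mg and placebo lack it. If only 30% (114) reach Week 52, that is 38 per arm: 38/45 = 84% of 3 mg have it, and 1 − 76/335 = 77% of 12 mg and placebo lack it.

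The order of enrolment makes the second calculation plausible, since (167 − 45)/167 = 73% of each large arm enrols after 3 mg closes. It remains an assumption.

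**4. Loss of precision, illustrated.** The standard error grows by about √(n primary / n per-protocol). Assume 380 enrolled evenly over 78 weeks (4.87 per week) and 15% dropout. None of this timing is in the documents.

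- Stop at week 78. Week 52 reached by those enrolled by week 26: 126.7 / 3 = 42.2 per arm; × 0.85 = 36. At least 24 weeks reached by those enrolled by week 54: 45 + (263.1 − 135)/2 = 109 per large arm; × 0.85 = 93. Ratio √(93/36) = 1.61.
- Stop at week 90. Week 52: 45 + (185.1 − 135)/2 = 70.1; × 0.85 = 60. At least 24 weeks: 45 + (321.5 − 135)/2 = 138.3; × 0.85 = about 118. Ratio √(118/60) = 1.40.

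**5. Power, and why no figure is offered as fact.** Effect size and SD are blacked out in Protocol 10.1.1. Back-solving from its power of at least 79% at up to 30% dropout, one-sided 0.10, with n = 167 × 0.7 = 116.9 per arm, gives d = (1.2816 + 0.8064)/√(116.9/2) = 0.273. Using Φ(0.273√(n/2) − 1.2816), the step 4 numbers give 72% at n = 93 and 79% at n = 118 for the primary analysis, against 45% at n = 36 and 58% at n = 60 for per-protocol. These rest on assumed timing and a back-solved effect.

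**6. The violation item.** The word *any* in 5.15 allows two readings. If it means missing the assessment at one or more scheduled visits, a patient stopped before Week 52 is a significant violator. If it means having no assessment at all, a patient with a baseline scan is not. The other items in 5.15 mirror the per-protocol conditions, which favours the first reading but does not settle it.

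**The case against.** **Other readings of the per-protocol condition.** It could mean each scheduled visit that the patient completed, or the ED column could count as scheduled. Protocol 9.1.1 describes the second scan as taken after 52 weeks or upon early discontinuation. Either reading would keep some terminated patients in. This stands as a reason to clarify. It does not remove the point, because the readings give different populations, and SAP 5.11.2 groups ED visits that do not match the schedule with unscheduled visits (for the repeated-measures model).

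**The restriction has merit.** Requiring Week 52 keeps the stated 52-week endpoint, whereas last-observation data mix durations. This stands, and is why completers should be kept as a named set. The per-protocol analysis is also only supportive, and version 2 already adds annualized tau PET change.

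**Stronger readings that the documents do not support.**

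- A reader might infer that most 12 mg and placebo patients are excluded while most 3 mg patients stay. The SAP speaks only of subjects overall, and the text alone allows 43% in those two arms (step 3).
- A reader might infer a fall in power from about 85% to 45–58%. The 85% comes from applying the back-solved effect to 167 × 0.85 = 142 per arm. It is not stated in the plan, and the comparison blames the per-protocol rule for patients already lost to termination.
- A reader might infer bias because selection follows calendar time. Allocation between 12 mg and placebo is equal throughout, so administrative truncation does not by itself unbalance that comparison. What is shown is lost precision.
- A reader might infer that 5.15 will be filled with patients who broke no rule. That depends on the reading of *any*. The clinical/medical group also has a part in determining violations, and a listing changes no estimate.
- The rater clauses have no evident object for a PET measure, but they exclude nobody.

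**Conclusion.** The point holds as a failure to carry the early-termination changes through. On the plain reading, the per-protocol set requires a scan that the SAP says a majority of patients lack, so fewer than half can qualify and the check becomes an analysis of Week 52 completers. It omits patients whose ED scan enters the primary analysis, and the cause is administrative. The overall size rests on the SAP's own statement and on reading the condition as baseline plus Week 52. Under the assumed timing in step 4, the standard error for 12 mg versus placebo would be about 1.4 to 1.6 times that of the primary analysis. That is an illustration and not an estimate for this trial. Whether 5.15 also mislabels patients stopped by the sponsor is open on its wording. The change should be made, but it does not threaten the primary analysis.

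**What to change.** - **Table LLCF.SAP.1, first per-protocol condition.** Replace with: has a baseline and at least one valid on-treatment post-baseline tau PET. State that a scan at the ED visit counts. This must be explicit, because SAP 5.6 removes data gathered after study drug is stopped from the per-protocol analysis.
- **Sensitivity set.** Keep Week 52 completers as a separately named population, so that a fixed 52-week contrast remains beside the last-observation results.
- **SAP 5.15, first item.** State whether it means missing one scheduled assessment or having none, and that scans missed because the sponsor stopped the study are not violations.
- **Optional.** Remove the rater clauses from the table and from 5.15. Results do not change.

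The cost is SAP wording, one more population flag and one more supportive table. No further data collection is needed.

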**Table LLCF.SAP.2. Efficacy and Safety Measures Summarized and/or Analyzed for Each Analysis Population**

Population Name	Variables Assessed
Enrolled	Listings
Efficacy	Tables, Listings and/or Figures of the following: subject disposition, subject characteristics, pre-existing conditions, significant historical diagnoses ADAS-Cog 13 , ADCS-iADL (and factor analyses), NPI, FAQ, ECog, BASQID, MoCA, MMSE, plasma A $\beta$ parameters, vMRI parameters, CSF parameters, AV-45 and Tau PET parameters and concomitant medications.
Safety Population	Tables, Listings and/or Figures of the following: Compliance, adverse events, laboratory results, vital signs, weight, ECG, MRI, skin examination, eye examination, and C-SSRS.
Per-Protocol Population	Tables, Listings and/or Figures of 18F-AV-1451 PET SUVr.

Abbreviations: ADAS-Cog13 = 13-item Alzheimer's Disease Assessment Scale – Cognitive subscale; ADCS-iADL = Alzheimer's Disease Cooperative Study-Activities of Daily Living inventory; BASQID = Bath Assessment of Subjective Quality of Life in Dementia; CSF = cerebrospinal fluid, C-SSRS = Columbia-Suicide Severity Rating Scale; ECG = electrocardiogram; ECog = Everyday Cognition; FAQ = Functional Activities Questionnaire; MMSE = Mini-Mental State Examination; MoCA = Montreal Cognitive Assessment; MRI = magnetic resonance imaging; NPI = Neuropsychiatric Inventory; PET = positron emission tomography; SUVr = standardized uptake value ratio.

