Patients who discontinue study treatment early should receive all early discontinuation procedures as described in Section 2. Patients should be encouraged to remain in the study until Week 52 (Visit 18), even if study treatment has been discontinued, and they should continue to participate in scheduled visits as described in Section 2. Patients who agree to remain in the study after discontinuing study treatment should continue to participate in scheduled visits and assessments, as appropriate, with the exception of PK measurements and PET scans, after completing the early discontinuation assessments described in Section 2, as appropriate. The follow-up visit (Week 56) is not required for patients who discontinue study treatment early and continue in the study, unless the study drug was discontinued within that last 4 weeks of the study. The Lilly-designated medical monitor may be consulted regarding the details of managing a specific patient who discontinues treatment but remains in the study.

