## 5.7. Subject Disposition

The protocol for this study makes the distinction between subject withdrawal and subject discontinuation of study treatment. Subject withdrawal occurs when a subject will no longer participate in the study (no longer taking study treatment and no longer being assessed). Subject discontinuation of study treatment occurs when a subject agrees to continue being assessed but will no longer take study treatment.

Reasons for discontinuation for all patients will be tabulated for treatment groups, and comparisons between treatment groups will be assessed by Fisher's exact test. Additionally, the median time to all-cause discontinuation will be compared between the treatment groups. The null hypothesis is that the median time to discontinuation estimated using the Kaplan-Meier product limit method will be identical for the LY3202626 dose groups and placebo. The log rank test will be used to test the null hypothesis against the alternate hypothesis that the median time to discontinuation is not the same between the groups.

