## 5.8. Subject Characteristics

Standard baseline characteristics of gender, age, and race will be summarized for all patients. Treatment group comparisons will be made using Fisher's exact test for categorical data and an ANOVA with an independent factor for treatment for continuous data. Diagnosis, illness characteristics, and baseline efficacy and safety measures will be analyzed in a similar manner.

Baseline characteristics will be summarized for the efficacy and per-protocol populations by treatment group and overall. Summaries will include descriptive statistics for continuous and categorical measures. Fisher's exact test or Pearson's chi-square test will be used for treatment-group comparisons of categorical data. For continuous data, analysis of variance (ANOVA),

with independent factors for treatment, will be used. Subject characteristics to be presented include:

- Baseline AV-45 SUVr
- Baseline Tau PET SUVr
- age
- age group: 55-64, 65-74, ≥75
- gender
- race
- ethnicity
- height
- body weight
- body mass index (weight (kg) / [height (m)])
- region
- tobacco use
- alcohol use
- years of education
- work status
- ApoE4 carrier status (carrier [ε2/ε4, ε3/ε4, ε4/ε4], noncarrier [ε3/ε3, ε2/ε2, ε3/ε2])
- ApoE4 genotype (ε2/ε4, ε3/ε4, ε4/ε4, no ε4)
- having 1 or more first degree relatives with AD
- AChEI and/or memantine use at baseline
- Baseline severity of impairment as measured by ADAS-Cog13, ADCS-iADL instrumental (ADCS-iADL) and , MMSE, MoCA, NPI, ECog, BASQID , and FAQ.

Baseline characteristics will also be listed.

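### Table LLCF.SAP.2 puts disposition and baseline tables on the Efficacy population, against the text of SAP 5.7 and protocol 10.3.2.1; if the table is followed, all-cause discontinuation is understated

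*SAP*

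**What the plan says.** Table LLCF.SAP.2 is introduced in SAP 5.6 as the list of what is summarized or analyzed in each population. Its Efficacy row begins "Tables, Listings and/or Figures of the following: subject disposition, subject characteristics, pre-existing conditions, significant historical diagnoses". Its Enrolled row contains one word, for listings.

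Table LLCF.SAP.1 defines the Efficacy population as "All randomized participants who take at least 1 dose of double-blind study treatment and have at least 1 postdose efficacy measurement". Enrolled means everyone randomized.

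Other text names a different population for the same tables:

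- SAP 5.7: "Reasons for discontinuation for all patients will be tabulated for treatment groups". Protocol 10.3.2.1 says the same. Both then add a Fisher test on reasons and a Kaplan-Meier and log-rank analysis of time to all-cause discontinuation.
- SAP 5.8, first paragraph: "Standard baseline characteristics of gender, age, and race will be summarized for all patients".
- SAP 5.8, second paragraph, which introduces the full list of characteristics: "Baseline characteristics will be summarized for the efficacy and per-protocol populations by treatment group and overall".
- SAP 5.1: "All analyses will follow the intent-to-treat (ITT) principle unless otherwise specified".

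**The concern.** A disposition table exists to account for everyone randomized. Membership of the Efficacy population depends on events after randomization: taking a dose, and staying or returning long enough to be measured. A table restricted to that population leaves out some of the patients it is meant to count.

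The time-to-discontinuation analysis has the same problem. The patients lost would be early leavers, so the Kaplan-Meier curve would sit too high over roughly the first 24 weeks.

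For baseline, comparability of the arms should be shown for the groups that randomization created. As written, the full baseline list by arm is specified only for two selected sets. The Per-Protocol set is narrower still, because it also requires the primary endpoint at each scheduled visit.

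Disposition carries more weight than usual here. SAP Section 3 records that the study ended early and that most subjects would lack a Week 52 observation.

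**Working it through.** **Which patients are affected.** The protocol's Schedule of Activities places the clinical scales after baseline at Week 24 (NPI and BASQID excepted), Week 52 and the ED visit. ED imaging is done only if at least 24 weeks have passed since the baseline measurement. Two groups can therefore lack a post-dose efficacy measurement:

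1. Patients randomized but never dosed. Protocol 10.1 foresees them and allows replacement.
2. Dosed patients who leave before Week 24 and have no ED efficacy measure, for example through death, loss to follow-up or refusal of the ED visit.

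**The plan's own figures.** The protocol gives about 380 enrolled, about 320 completers and about 15% dropout. 320/0.85 = 376.5, rounded up to 377, against 380 stated. In the other direction, 380 × 0.85 = 323, against 320 stated. Both agree within rounding. The other stated rate is the 30% upper dropout scenario in protocol 10.1.1.

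**Effect of the population.** Let N be the number randomized, D the number who discontinue, and e the number of discontinuers outside the Efficacy population.

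- Rate on Enrolled: D/N
- Rate on Efficacy: (D-e)/(N-e)
- Difference: D/N - (D-e)/(N-e) = e(N-D)/[N(N-e)], which is positive whenever e > 0 and D < N

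With d = D/N and s = e/D, the rate on Efficacy is d(1-s)/(1-sd). The documents do not give s. The range of 10% to 35% is an assumption.

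| True rate d | s | Calculation | Reported rate |
|---|---|---|---|
| 15% | 0% | 0.15/1 | 15.0% |
| 15% | 10% | 0.135/0.985 | 13.7% |
| 15% | 35% | 0.0975/0.9475 | 10.3% |
| 30% | 10% | 0.27/0.97 | 27.8% |
| 30% | 35% | 0.195/0.895 | 21.8% |

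Check in whole patients: 15% of 380 is 57. With e = 6, 51/374 = 13.6%. With e = 20, 37/360 = 10.3%.

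The understatement is 1.3 to 4.7 percentage points at 15% and 2.2 to 8.2 points at 30%. It is zero if e = 0.

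**The case against.** **The specific section should govern.** SAP 5.7 specifies the disposition analysis, the protocol agrees with it, and Table LLCF.SAP.2 can be read as an index. This stands in part. A reader might infer from the table that the plan has decided to leave early leavers out, and the documents do not support that. But the SAP gives no rule of precedence between table and text, and the intent-to-treat default yields wherever something else is specified. For baseline the conflict is not confined to the table, since the second paragraph of 5.8 repeats the restriction.

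**The ED visit captures early leavers.** Protocol 8.1.1 says: "Patients who discontinue study treatment early should receive all early discontinuation procedures as described in Section 2". Protocol 8.2 provides an ED visit for those who leave the study, and the schedule marks all the clinical scales there. One completed ED scale puts a dosed patient in the Efficacy population. This stands, so it would be wrong to say that early dropouts as a class are removed. It makes e smaller but does not make it zero.

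**Safety failures are counted elsewhere.** SAP 5.13.2 and 5.13.3 summarize deaths, serious events and discontinuations due to adverse events, and SAP 5.6 puts safety summaries on the Safety population. This also stands: an excess of adverse-event withdrawals among dosed patients would remain visible. Withdrawal of consent, loss to follow-up and never-dosed patients are not covered there, and the all-cause comparison has no Safety-population version.

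**Two further readings are not supported.** One is that a real difference between arms would be hidden. The documents give neither discontinuations nor missing ED measures by arm, so no effect on the comparison can be sized. The other is that early plasma Aβ samples are lost. Protocol 10.3.1 assigns pharmacodynamic analyses to the efficacy population unless otherwise specified, and neither document says whether plasma Aβ, sampled from Week 2, counts as an efficacy measurement. If it does, e is smaller still.

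**Conclusion.** The point holds as an internal contradiction with a known direction of error. Table LLCF.SAP.2, and for baseline the second paragraph of SAP 5.8, name a population that conflicts with SAP 5.7, the first paragraph of SAP 5.8 and protocol 10.3.2.1. If the table is followed, all-cause discontinuation is understated whenever e > 0.

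The size cannot be fixed from the documents. The range of 13.7% to 10.3% for a planned 15% rests on three assumptions: the 10% to 35% share, every excluded patient being a discontinuer, and the planning rate. Because the study ended early, that rate may not describe the data this SAP will analyze.

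The defect concerns disposition and baseline tables. It does not change the population for the primary endpoint or for the safety summaries.

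**What to change.** 1. In Table LLCF.SAP.2, move subject disposition and subject characteristics from the Efficacy row to the Enrolled row, and let that row cover tables and figures as well as listings.
2. In SAP 5.7, state that reasons for discontinuation, the Fisher test and the Kaplan-Meier and log-rank analysis use the Enrolled population.
3. In SAP 5.8, present the full baseline list by arm on the Enrolled population, and keep the Efficacy and Per-Protocol baseline tables as supplementary.

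This brings the table into line with SAP 5.7 and protocol 10.3.2.1. The cost is a table edit, two sentences and a population flag in the programs. No new data are needed.
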